5.7. Other Analyses

5.7.1. Immunogenicity

The PPI-A set will be used for analysis of immunogenicity for adult participants and the PPI-NVN set will be used for neonates/infant.

Selected immunogenicity analyses will also be done on the FAS-A and FAS-NVN. Participants who become infected during the study or receive another COVID-19 vaccine outside of the study will be analyzed as subgroups and identified in graphs using specific colors and symbols. Data will be analyzed separately for adult participants and for neonates/infants.

Key immunogenicity assay data from other studies may be used in selected graphs and tables, for descriptive comparison of immunogenicity results in pregnant women from COV2004 vs non-pregnant women in other Janssen Ad26.COV2.S studies. Reference to the respective study will be added and clearly indicated in those tables and graphs.

Key immunogenicity assay results (S-ELISA, VNA) will also be analyzed for the subgroups defined in Section 5.7.4.

CONFIDENTIAL – FOIA Exemptions Apply in U.S.

Data will be presented by scheduled time point. For inclusion of immunogenicity samples taken outside of the allowed windows, see section 5.1.3. For the FAS-A and FAS-NVN analyses, samples taken outside of the allowed window will be included.

Categorical variables will be summarized with a frequency table showing counts and percentages. Continuous variables will be summarized using the following statistics, as appropriate: number of observations, geometric mean, 95% confidence interval (CI) for geometric mean, arithmetic mean (mean), 95% CI for the mean, standard deviation (SD), standard error (SE), median, quartiles (Q1 andQ3), minimum and maximum.

Data listings, participant profiles and/or participant narratives may be provided as appropriate. Binary variables will be summarized using the following statistics: number of observations, percentages, and Exact Clopper-Pearson 95% CIs.

5.7.1.1. Parameters

For adults, the assays planned include (but are not limited to): S-ELISA, psVNA, wtVNA (if feasible), Ad26 VNA (if feasible), MesoScaleDiscovery (MSD) 4-plex, ADCP (if feasible) and ICS (if feasible). For neonates/infants, the assays planned include (but are not limited to): S-ELISA, psVNA, and MSD 4-plex. Others, wtVNA (if feasible), Ad26 VNA (if feasible), and ADCP (if feasible) may also be performed in cord blood. However, not all assays might be available for all immunogenicity analyses covered by this SAP. Some of the exploratory immunogenicity endpoints mentioned in this section will only be considered as potential assessment for analyses after the primary analysis is performed, as described in Section 1.1. The humoral and cellular immune responses described in Table 5 may be measured.

Summary of Humoral Immunogenicity Assays			
Assay	Purpose		
Primary/Secondary endpoints			
SARS-CoV-2 binding antibodies (ELISA)	Analysis of antibodies binding to the SARS-CoV-2 S protein		
SARS-CoV-2 neutralization (VNA)	Analysis of neutralizing antibodies to the wild-type and/or pseudovirion expressing S protein		
Exploratory endpoints			
SARS-CoV-2 binding antibodies (ELISA and/or SARS-CoV-2 immunoglobulin assay)	Analysis of antibodies binding to the SARS-CoV-2 Spike (S) protein, nucleocapsid (N) protein, receptor binding domain (RBD) of the SARS- CoV-2 S protein, or other proteins, including surface proteins of other coronaviruses		
SARS-CoV-2 neutralization (VNA)	Analysis of neutralizing antibodies to the wild-type virus, viral variants, and/or pseudovirion expressing S protein		
ELISA or Ig assay detecting coronavirus-specific antibodies	Analysis of antibodies binding to coronaviruses other than SARS-CoV-2, or other respiratory viruses		
Antibodies specific to coronaviruses or other respiratory viruses (MSD)			

 Table 5:
 Summary of Humoral and Cellular Immunogenicity Assays

Assay	Purpose	
SARS-CoV-2 binding immunoglobulins, including IgA antibodies (ELISA)	Analysis of IgA and/or other Ig subtypes against SARS-CoV-2 in breast milk	
SARS-CoV-2 binding immunoglobulins, including IgA antibodies (ELISA)	Analysis of IgA and/or other Ig subtypes against SARS-CoV-2 in colostrum	
Adenovirus neutralization (neutralization assay)	Analysis of neutralizing antibodies to adenovirus	
Functional and molecular antibody characterization	Analysis of antibody characteristics including Fc-mediated viral clearance, avidity, Fc characteristics, Ig subclass and IgG isotype, antibody glycosylation, and assessment of antibody repertoire.	
Epitope-specificity characterization	Analysis of site-specificity, epitope mapping	
Cytokine profiling, metabolomics and/or lipidomics	Analysis of cytokines, chemokines, and other proteins, metabolites or lipid mediators of the innate or adaptive immune response in the serum or plasma	
Passive transfer	Analysis of immune mediators correlating with protection against experimental SARS-CoV-2 challenge in a suitable animal model	
Transcriptional analysis of vaccine-induced Biomarkers	Analysis of mRNA expression levels of vaccine-induced biomarkers of immune mediated responses.	
Transcriptional analysis of vaccine-induced innate immunity and inflammatory responses	Analysis of mRNA expression levels of vaccine-induced innate responses, including inflammatory mediators.	

Summary of Humoral Immunogenicity Assays

ELISA = enzyme-linked immunosorbent assay; Ig = immunoglobulin; MSD = Meso Scale Discovery; SARS-CoV 2 = severe acute respiratory syndrome coronavirus-2; VNA = virus neutralization assay

Assay	Purpose
Exploratory endpoints	
Flow cytometry (ICS)	Analysis of T-cell responses to SARS-CoV-2 S protein, and/or other protein peptides by ICS including CD4 ⁺ /CD8 ⁺ , IFNγ, IL-2, TNFα, IL-4, IL-5, IL-13, and/or other Th1/Th2 markers
ELISpot	IFNγ and IL-4 responses to SARS-CoV-2 S protein peptides by PBMCs, based on single or dual ELISpot
Gene expression analysis	Analysis of gene expression by RNA transcript profiling and/or analysis of protein translates, in cells or whole blood stimulated with SARS-CoV-2 S protein peptides or in unstimulated cells or whole blood (ex vivo)
Cytokine profiling (ELISA or multiplexed arrays)	Analysis of cytokines, chemokines, and other proteins of the innate or adaptive immune response in cells or whole blood stimulated with SARS-CoV-2 S protein peptides, or in unstimulated cells or whole blood, by ELISA or multiplexed arrays and confirmation by functional in vitro assays
T and B cell phenotyping	Analysis of the phenotype of antigen-specific T and B cells, assessed by single cell analysis

Summary of Cellular Immunogenicity Assays

CD = cluster of differentiation; ELISA = enzyme-linked immunosorbent assay; ELISpot = enzyme-linked immunosopt (assay); ICS = intracellular cytokine staining; IFN γ = interferon gamma; IL = interleukin; PBMC = peripheral blood mononuclear cell; RNA = ribonucleic acid; SARS-CoV-2 = severe acute respiratory syndrome coronavirus-2; Th = T helper; TNF α = tumor necrosis factor alpha; VNA = virus neutralization assay.

Handling of Missing and/or Unguantifiable Immune Response Data 5.7.1.2.

Missing immune response data will not be imputed.

Values below the lower limit of quantification (LLOQ) or limit of detection (LOD) will be handled as follows:

- Calculation of geomean and median:
 - values<LLOQ are imputed with LLOQ/2.
- Calculation of fold changes from baseline:
 - values <LLOQ are imputed with LLOQ.

Values above the upper limit of quantification (ULOQ) will be handled as follows:

- Calculation of geomean and median:
 - Values>ULOQ are imputed with ULOQ.
- Calculation of fold changes from baseline:
 - Values >ULOQ are imputed with ULOQ.

5.7.1.3. Handling of Changes in Assay Status throughout the Study Conduct

In case of changes in assay status, from "qualified" to "validated", the LLOQ and ULOQ are likely to change as well. If this should happen, then the SDTM database will contain records pertaining to the assay in the qualified status and records pertaining to the validated status, and the LLOO and ULOQ values will also differ.

The statistical analysis will use the LLOQ and ULOQ values associated with the validated assay and will retrospectively apply these on all the data pertaining to the assay, including the data obtained while the assay status was "qualified". This may imply that data received, statistically analyzed, and presented at an earlier time may change. Graphical displays will show the eventually used LLOQ and ULOQ values. Graphs and tables will have an additional footnote, that reflects the assay status.

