5.7.1.5. Immunogenicity Against the Insert

5.7.1.5.1. Humoral Assays

For **VNA** (both wild-type virus and pseudovirion expressing S protein, as available), the following statistics will be calculated: N, geometric mean, and corresponding 95% CI of the actual values, fold change from baseline and fold change from pre-booster (for time points after booster vaccination). In some cases, fold change from other timepoints may also be calculated. Geometric mean ratio and CI will be calculated at each post baseline visit.

For the calculation of the geometric mean and its corresponding 95% CI, the arithmetic mean, and its corresponding 95% CI are calculated on the log₁₀ transformed values. These values are back transformed to provide the geometric mean and its corresponding 95% CI.

For wild-type and pseudovirion VNA separately:

- A sample will be considered positive if the value is strictly greater than the LLOQ (>LLOQ).
- Responder definition (in adults): A post-baseline sample will be considered a responder if at least one of the following conditions is satisfied:
 - $\circ~$ The baseline sample value is less than or equal to the LLOQ (\leq LLOQ) and the post-baseline sample value is strictly greater than the LLOQ (>LLOQ)
 - The baseline sample value is strictly greater than the LLOQ (>LLOQ) and the post-baseline value represents an at least 4-fold (\geq 4-fold) increase from the baseline sample value.

Actual values are tabulated and shown as dot plots with dots for participant values, and the corresponding geometric mean and 95% CI per time point for each assay. In addition, GMT plots over time without individual participant dots will also be generated. Participant profiles of the actual values over time will be graphically presented.

For infants born to vaccinated mothers, tables and graphs will be made per the vaccine regimen of the mother. In addition, in the neonate profiles of the actual values over time, the mother's value at birth will be added to visualize transfer of binding or neutralizing antibodies to the newborn.

In the graphs, original values will be displayed on the log_{10} scale.

Further details and/or updated rules will be provided in the DPS.

For the exploratory **variant SARS-CoV-2 neutralization assays** (different from the VNA used for the secondary endpoint), the same as above applies.

For **S-ELISA** and **MSD 4-PLEX**, the same as above applies.

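### Validated assay limits are applied retrospectively without condition, which misplaces qualified-era results held only as below LLOQ or above ULOQ if the validated range is wider

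*SAP*

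**What the plan says.** SAP section 5.7.1.3 covers a change of assay status from qualified to validated. It expects that in that event "the LLOQ and ULOQ are likely to change as well" and that the database will hold records of both kinds. The rule is then: "The statistical analysis will use the LLOQ and ULOQ values associated with the validated assay and will retrospectively apply these on all the data". The sentence goes on to include results produced in the qualified period. The section accepts that results already presented may change, and it requires graphs to show the limits used and outputs to carry a footnote on assay status. It does not separate a wider validated range from a narrower one, mentions no re-testing, and makes no exception for results without a numeric value.

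Three other rules take their limits from this one:

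- **Imputation (5.7.1.2).** For the geometric mean and median, "values<LLOQ are imputed with LLOQ/2". For fold change from baseline, the substitute is the LLOQ itself. At the top, "Values>ULOQ are imputed with ULOQ".
- **Positivity (5.7.1.5.1).** The cut-off is the LLOQ, exclusive.
- **Response (5.7.1.5.1).** With a baseline at or below the LLOQ, any later value above the LLOQ is a response. With a baseline above it, at least a 4-fold rise is needed.

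These rules are written for the VNA and extended to S-ELISA and MSD 4-plex. S-ELISA at 28 days after vaccination is the primary immunogenicity endpoint (5.3.1).

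**The concern.** A result reported only as below a limit says one thing: the value is under that limit. If the limit later falls, the result no longer says on which side of the new limit the sample lies. The rule nevertheless treats it as below the new limit, imputes it from there, and calls it negative. The same happens at the top when the ULOQ rises.

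Fold change is the most exposed quantity. Imputing a censored baseline at the LLOQ it was tested against is conservative: the true baseline is no higher, so the computed rise cannot exceed the true one. Imputing it at a lower limit that it was never tested against removes that protection. Response is exposed as well: a woman with a censored baseline becomes a responder on any later value above the new LLOQ, although with a numeric baseline she might have needed a 4-fold rise.

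**Working it through.** **Inputs.** From the SAP: the retrospective rule (5.7.1.3), the imputation rules (5.7.1.2), and the positivity and response rules (5.7.1.5.1). The SAP gives no LLOQ or ULOQ for S-ELISA, VNA or MSD, no direction of change, and no statement on how out-of-range humoral results are stored. It states no figure on this point to reproduce. Assumed: r = validated LLOQ / qualified LLOQ of 0.8, 0.5 or 0.25, and a share p of results held only as below the old LLOQ.

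**Step 1: which cases are ambiguous.** Write L for the qualified LLOQ.

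- Validated LLOQ higher than L: a result below L is also below the new limit. No ambiguity.
- Validated LLOQ lower, numeric value stored: the value is compared directly with the new limit. No ambiguity.
- Validated LLOQ lower, only below-L known: the value may lie on either side of rL. Ambiguous.

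The ULOQ cases mirror these.

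**Step 2: shift in the geometric mean.** A censored result moves from L/2 to rL/2, a change of log10(r) on the log scale. Over a share p, the mean log moves by p·log10(r), so the geometric mean is multiplied by r^p.

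**Step 3: shift in the fold rise.** A censored baseline moves from L to rL in the denominator. With measured post-baseline values, the geometric mean fold rise is multiplied by (1/r)^p.

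| r | Quantity | p = 25% | p = 50% | p = 75% |
|---|---|---|---|---|
| 0.8 | Fold rise | 1.057 | 1.118 | 1.182 |
| 0.8 | Geometric mean | 0.946 | 0.894 | 0.846 |
| 0.5 | Fold rise | 1.189 | 1.414 | 1.682 |
| 0.5 | Geometric mean | 0.841 | 0.707 | 0.595 |
| 0.25 | Fold rise | 1.414 | 2.000 | 2.828 |
| 0.25 | Geometric mean | 0.707 | 0.500 | 0.354 |

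At the top, a ULOQ raised by a factor R multiplies the geometric mean by R^p. For R = 2 and 10% or 25% of results above the old ULOQ, that is 1.07 or 1.19.

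**Step 4: one participant.** Take r = 0.5, a true baseline of 0.8L reported only as below L, and an unchanged later value of 0.8L measured in the validated assay. The rule gives a fold change of 0.8L / 0.5L = 1.6 and calls her a responder, because 0.8L exceeds 0.5L. The true fold change is 1. With a numeric baseline she would have needed 4 × 0.8L = 3.2L. This false response requires two eras, since a later value between 0.5L and L can be reported only by the validated assay. The shift in the fold-change denominator requires only the censored older baseline and a measured later value.

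**Step 5: simulation.** Assumptions: log-normal baselines with log10 SD 0.4 to 0.8, 25% to 75% of them censored at L, and post-baseline values from the validated assay with a 2-fold mean rise (log10 SD 0.3).

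| | r = 0.5 | r = 0.25 |
|---|---|---|
| Censored results truly above the new LLOQ | 18% to 70% | 38% to 94% |
| Responder rate, numeric baselines and new LLOQ | 19% to 32% | 17% to 26% |
| Responder rate, SAP rule with censored baselines | 28% to 54% | 32% to 69% |
| Responder rate, higher LLOQ for all results | 19% to 33% | 19% to 33% |

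**Step 6: geometric mean alone.** With SD 0.4 and 50% censored, L/2 gives 1.02 times the true mean, while rL/2 gives 0.72 (r = 0.5). With SD 0.8 and 75% censored, L/2 gives 2.70 times the true mean, while rL/2 gives 1.61 (r = 0.5) or 0.96 (r = 0.25). Neither imputation is closer throughout.

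**The case against.** Several things must coincide: the assay changes status during the study, the range widens, older out-of-range results have no number, and compared samples fall in different eras. The SAP establishes none of these. Its remark that limits are likely to change is conditional on a status change and gives no direction.

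A reader might infer that the rule is wrong whenever the validated range is wider. The SAP does not support that. With stored numbers the rule works, and elsewhere the SAP implies that values below a limit can be held. ICS values under 0.022% are replaced for display only, and IL-4 ELISpot uses separate LOD and LLOQ conditions (5.7.1.5.2). These are cellular assays, so they do not settle S-ELISA or VNA. Section 5.6.2, by contrast, explicitly handles safety laboratory results that have no number and imputes them from the cut-off reported with each result. The immunogenicity sections do not say which situation applies.

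A reader might also infer that the affected results are mostly baseline samples or those of early-enrolled women. Era depends on when a sample is tested, and no testing schedule is given. If a woman's samples are run together, the false response in Step 4 does not arise.

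It is fair to add that no hypothesis is tested, that limits and assay status will be displayed, and that 5.7.1.5.1 defers further or updated rules to the Data Presentation Specifications, which are not at hand. Displaying the limits does not recover the position of a censored result, however, and the rule as written remains unconditional.

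**Conclusion.** The point holds as a conditional one. The rule is sound for a narrower validated range or where numeric values are stored. It misfires in a foreseeable case that it does not exclude: a wider range with older results known only as out of range. The outputs at risk are descriptive fold rises, positivity and responder rates, including those for the primary Day 29 S-ELISA response.

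The size depends on assumed limits and censoring. For 25% to 75% of baselines censored, the fold rise is inflated by about 6% to 18% with the LLOQ at 0.8 of its old value, and by 19% to 68% with it halved. It would be tempting to say that fold rises change by the full ratio of the limits, for example double when the LLOQ halves. That is the extreme in which every baseline is censored, and it is not a natural assumption for S-ELISA in Groups 1 to 3, who were vaccinated before entry. Nor can the geometric mean alone be called biased in a known direction: in some simulated settings the lower imputation came closer to the truth.

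**What to change.** Add to SAP section 5.7.1.3, before database lock, a condition taken separately for each assay and each limit:

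- Validated limits are applied retrospectively where the validated range is narrower, or where numeric values beyond the qualified limits are available. State for each assay whether such values are retained.
- Otherwise, for comparisons that mix assay eras, use the higher of the two LLOQs and the lower of the two ULOQs for imputation, positivity and responder status. Comparisons run wholly in one era keep that era's limits.

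With the higher LLOQ, the factors in Steps 2 and 3 return to 1 for the censored older results. The cost is a short addition to the text and some loss of information: values measured by the validated assay that lie between the old and new limits are treated as censored in mixed comparisons.

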5.7.1.4. Immune Response Analysis

No formal hypothesis on immunogenicity will be tested.

5.7.1.5. Immunogenicity Against the Insert

5.7.1.5.1. Humoral Assays

For **VNA** (both wild-type virus and pseudovirion expressing S protein, as available), the following statistics will be calculated: N, geometric mean, and corresponding 95% CI of the actual values, fold change from baseline and fold change from pre-booster (for time points after booster vaccination). In some cases, fold change from other timepoints may also be calculated. Geometric mean ratio and CI will be calculated at each post baseline visit.

For the calculation of the geometric mean and its corresponding 95% CI, the arithmetic mean, and its corresponding 95% CI are calculated on the log₁₀ transformed values. These values are back transformed to provide the geometric mean and its corresponding 95% CI.

For wild-type and pseudovirion VNA separately:

- A sample will be considered positive if the value is strictly greater than the LLOQ (>LLOQ).
- Responder definition (in adults): A post-baseline sample will be considered a responder if at least one of the following conditions is satisfied:
 - $\circ~$ The baseline sample value is less than or equal to the LLOQ (\leq LLOQ) and the post-baseline sample value is strictly greater than the LLOQ (>LLOQ)
 - The baseline sample value is strictly greater than the LLOQ (>LLOQ) and the post-baseline value represents an at least 4-fold (\geq 4-fold) increase from the baseline sample value.

Actual values are tabulated and shown as dot plots with dots for participant values, and the corresponding geometric mean and 95% CI per time point for each assay. In addition, GMT plots over time without individual participant dots will also be generated. Participant profiles of the actual values over time will be graphically presented.

For infants born to vaccinated mothers, tables and graphs will be made per the vaccine regimen of the mother. In addition, in the neonate profiles of the actual values over time, the mother's value at birth will be added to visualize transfer of binding or neutralizing antibodies to the newborn.

In the graphs, original values will be displayed on the log_{10} scale.

Further details and/or updated rules will be provided in the DPS.

For the exploratory **variant SARS-CoV-2 neutralization assays** (different from the VNA used for the secondary endpoint), the same as above applies.

For **S-ELISA** and **MSD 4-PLEX**, the same as above applies.

The ratio of binding antibodies (S-ELISA measured by S-ELISA or MSD 4-PLEX assay) to wild type VNA, the ratio of binding antibodies (S-ELISA measured by S-ELISA or MSD 4-PLEX assay) to pseudovirion expressing S protein VNA, and the ratio of binding antibodies (S-ELISA measured by S-ELISA or MSD 4-PLEX assay) to the VNAs measured by alternative assays will be calculated for each time point. Values <LLOQ will be imputed with LLOQ for the calculation of the ratios. In addition, the ratio of the fold change from baseline in binding antibodies (S-ELISA measured by S-ELISA or MSD 4-PLEX assay) to the fold change from baseline in VNA, will be calculated for each post-baseline time point. Values <LLOQ will be imputed with LLOQ for the calculated for each post-baseline time point. Values <LLOQ will be imputed with LLOQ for the calculation of the fold change ratios. The following statistics will be calculated and tabulated: N, geometric mean and corresponding 95% CI of the ratio. Graphical displays will also be prepared, showing – for each time point – the geometric mean of the ratio and its 95% CI, together with the individual data points (dot plot).

If a similar assay is performed at different analyzing labs, then separate statistical analyses may be performed.

Scatterplots between humoral assay results (as available) will be provided for selected time points. These may be included but are not limited to:

- Binding antibodies (S-ELISA measured by S-ELISA or MSD 4-PLEX assay) versus VNA (wild type VNA, psVNA or variant VNA)
- wtVNA versus psVNA
- wtVNA versus variant VNA
- psVNA versus variant VNA
- Ad26 VNA versus S-ELISA
- Ad26 versus wtVNA
- Ad26 versus psVNA and/or variant VNA

If a similar assay is performed at different analyzing labs, then the statistical analyses may distinguish between these and provide separate scatterplots for each analyzing lab versus the other assay of interest. These scatterplots will display the values as analyzed for the geometric mean calculations, with values <LLOQ imputed with LLOQ (if an LLOQ is defined) and values >ULOQ imputed with ULOQ (if an ULOQ is defined). The LLOQ and ULOQ cut-off values per assay will be visualized in the scatterplots. Spearman correlation coefficients will also be provided (one per scatterplot).

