5. STATISTICAL ANALYSES

5.1. General Considerations

A baseline (or reference) value will be defined as the value of the last available assessment prior to the first vaccination on Day 1, where Day 1 is the date of first vaccination for adults. A value at birth is baseline value for neonates and the birth date is the neonate reference date. The neonate baseline values for immunogenicity analysis are those from the cord blood sample collected.

Every adult will have a unique subject ID in the ADaM datasets and every neonate will have the same unique subject ID with 'A' added at the end of the ID. Multiple pregnancies [twins or higher order multiples] are excluded from the study but if a participant with multiple pregnancy is inadvertently enrolled, neonates will have the same unique subject ID with 'A', 'B', 'C' and D added at the end of the ID based on the number of neonates.

Unless otherwise specified, continuous variables will be summarized using the following statistics, as appropriate: number of observations, arithmetic mean (mean), standard deviation (SD), standard error (SE), median, minimum, and maximum. Frequencies and percentages (one decimal place) will be generated for categorical variables. Denominator for the percentages is the number of participants in the considered population, and phase (where applicable; incidence per 100 participants/phase).

No formal statistical testing is planned. The safety analysis will be performed on the FAS-A based on actual intervention received and the FAS-NVN, unless otherwise specified. Safety data will be presented by period/phase (as applicable) as well as over the entire study. Immunogenicity results will be conducted on the PPI-A and PPI-NVN and presented per scheduled time point as appropriate. Safety and immunogenicity endpoints will be summarized descriptively by previous vaccination group (as defined in Section 1.2) and overall. All listings will include the previous vaccination group. Vaccination schedule in Group 4 (i.e. vaccine-naive at study entry) will have two components: the Primary Vaccination and the (optional) Booster Vaccination. Listings will be shown per phase and time point, as appropriate.

Participants that took another COVID-19 vaccine during the study are excluded from all safety and immunogenicity analyses from the moment they received the other vaccine. The safety data from those participants after they received the other vaccine will be listed separately.

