- Serological response to vaccination measured by binding (S-ELISA and/or equivalent assay) and neutralizing (VNA) antibody titers pre-boost and at selected time points post-booster vaccination.

Antibody levels against SARS-CoV-2 in neonates/infants

- Serological response to vaccination as measured by ELISA (S-ELISA, EU/mL) at birth (i.e., in cord blood) and at approximately 2 months, and 6 months of age.
- Serological response to vaccination as measured by VNA titers at birth (i.e., in cord blood).

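### After the booster, the humoral responder rule still looks back to the value before dose 1, so a post-booster responder rate is cumulative since study entry and does not isolate the booster

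*SAP*

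**What the plan says.** Section 5.1 fixes one baseline per adult: "A baseline (or reference) value will be defined as the value of the last available assessment prior to the first vaccination on Day 1". No separate baseline is defined for the booster.

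Section 5.7.1.5.1 defines the adult responder for the wild-type and pseudovirion VNA: "A post-baseline sample will be considered a responder if at least one of the following conditions is satisfied". The first condition is baseline at or below LLOQ and post-baseline above it. The second is baseline above LLOQ, "and the post-baseline value represents an at least 4-fold" increase over baseline. For variant neutralization, S-ELISA and MSD 4-PLEX, "the same as above applies". Nothing sets post-booster samples apart.

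The same section does re-reference the fold change. It plans "fold change from baseline and fold change from pre-booster (for time points after booster vaccination", summarised by geometric mean and 95% CI.

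The booster is offered to vaccine-naïve women (Group 4) no earlier than 2 months after the first study dose (section 1.2). Their humoral response to it is a secondary objective (section 1.1), and section 5.4.1 describes the endpoint by binding and neutralizing "antibody titers pre-boost and at selected time points post-booster vaccination". Section 5.7.1 says that binary variables are summarised as percentages with exact Clopper-Pearson intervals.

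**The concern.** A post-booster sample is a post-baseline sample, so the rule as written covers it. Because baseline precedes dose 1, the comparison spans both doses. A Group 4 woman who was at or below LLOQ on Day 1 is a post-booster responder whenever her value exceeds LLOQ, and persisting dose-1 antibody can achieve that alone. A woman above LLOQ on Day 1 qualifies if dose 1 left her at least 4-fold higher.

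A reader who meets a responder percentage at the post-booster visit, under a secondary objective about the booster, will naturally take it as the share of women who responded to the booster. With persisting dose-1 antibody it may be high for an inert booster, and it will change little between an effective and an ineffective one.

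**Working it through.** The SAP states no responder rate, LLOQ, titre or SD, so there is no figure of its own to reproduce.

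**Step 1: the rule applied literally, no distribution assumed.** Titres are in multiples of LLOQ, and the booster multiplies the titre by exactly 1.

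| Day 1 | Pre-booster | Post-booster | Rule as written | Same rule, pre-booster reference |
|---|---|---|---|---|
| 0.5 | 8 | 8 | responder | not |
| 2 | 16 | 16 | responder (16/2 = 8-fold) | not |
| 0.5 | 1.5 | 1.5 | responder | not |
| 0.5 | 0.8 | 0.8 | not | not |
| 2 | 6 | 6 | not (6/2 = 3-fold) | not |

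The first three rows show the fault. The last two show its limit: dose-1 antibody must still meet the threshold at the post-booster visit.

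**Step 2: how often, under assumed titres.** These inputs are assumptions, not SAP figures: all women at or below LLOQ on Day 1; pre-booster geometric mean G of 1 to 16 times the LLOQ; between-woman log10 SD of 0.4 or 0.6; assay log10 SD of 0.1; booster multiplier m of 1 (inert) or 8.

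For these women the written rule reduces to post-booster titre above LLOQ, so

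P(responder) = Φ( log10(m × G) / s ), with s = √(between-woman SD² + assay SD²).

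Here s = √(0.16 + 0.01) = 0.412 or √(0.36 + 0.01) = 0.608. Example: G = 8 and m = 1 give Φ(0.903/0.412) = 98.6% and Φ(0.903/0.608) = 93.1%. The pre-booster version compares two noisy readings and was simulated with 400,000 women per setting. The simulation also reproduced the closed form for the written rule.

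Each cell shows between-woman SD 0.4 / SD 0.6.

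| G | As written, m = 1 | As written, m = 8 | Pre-booster reference, m = 1 | Pre-booster reference, m = 8 |
|---|---|---|---|---|
| 1 | 50% / 50% | 99% / 93% | 5% / 4% | 97% / 92% |
| 2 | 77% / 69% | >99% / 98% | 4% / 3% | 98% / 96% |
| 4 | 93% / 84% | >99% / 99% | 2% / 2% | 98% / 98% |
| 8 | 99% / 93% | >99% / >99% | 0.5% / 1% | 98% / 98% |
| 16 | >99% / 98% | >99% / >99% | 0.1% / 0.5% | 98% / 98% |

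Under the written rule, the gap between an 8-fold and an inert booster falls from 43-49 percentage points at G = 1 to 0.2-2.4 points at G = 16. With the pre-booster reference it stays at 88-98 points throughout.

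**Step 3: sensitivity.**
- Assay SD 0.15, between-woman SD 0.4-0.5, pre-booster mean 0.2-1.2 log10 above LLOQ: the written rule gives 65%-99.8% for an inert booster and 98%-100% for an 8-fold one. The pre-booster reference gives 0.4%-7% and about 92%-93%.
- Group 4 is vaccine-naïve, not necessarily seronegative (Table 7 allows a positive result). With the Step 2 SDs, suppose 30% of women are above LLOQ on Day 1, with geometric mean 4 times the LLOQ and a geometric mean rise of 1- to 16-fold after dose 1. The written rule then gives 38%-98% for an inert booster, and the pre-booster reference 0.1%-4.6%.

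**The case against.** The strongest reply is that the booster increment is already planned for. The fold change from pre-booster, with its confidence interval, is specified for VNA and carried to the other humoral assays, and an inert booster would show a geometric mean near 1. The secondary endpoint is worded in terms of titres, not a responder rate. No post-booster responder table is named; it is inferred from the wording of the rule and the general sentence on binary variables. A response counted from Day 1 is a legitimate cumulative description. The SAP also defers further or updated rules to the DPS. All of this stands, and it limits the point to the responder rate. The DPS is not available here, so it cannot be taken as having settled the matter.

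A reader might go further and infer that the responder rate cannot separate an effective booster from an inert one, or that the booster objective goes unanswered. The documents do not support either. At low pre-booster titres the written rule does separate the two (65% against 98% in the lowest case of the second set of assumptions). The pre-booster sample is itself post-baseline, and if the rate is tabulated at every visit, an inert booster would leave it roughly unchanged from that visit, apart from waning. Nor can it be said that dose 1 will produce a post-booster responder, only that it can.

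**Conclusion.** The point holds as a gap in one derived variable. The only humoral responder rule refers to the value before dose 1, so a post-booster rate in Group 4 is cumulative since study entry and credits persisting dose-1 antibody. That much follows from the text and needs no assumption. The size does: for an inert booster the rate runs from about 38% to nearly 100% over the titre distributions tried, and discrimination is lost mainly when pre-booster titres are high.

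The stakes are modest. The analysis is descriptive, so no error rate or decision rule is affected. The primary S-ELISA endpoint, 28 days after the first vaccination, uses the Day 1 baseline properly. The booster is optional and confined to Group 4, whose minimum target was 25. The change is still worth making, because it is cheap and prevents a misreading of a secondary result.

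**What to change.** In section 5.7.1.5.1, add for time points after the booster: a sample is a booster responder if the pre-booster value is at or below LLOQ and the post-booster value is above LLOQ, or if the pre-booster value is above LLOQ and the post-booster value is at least 4-fold higher than it. Apply this to the same assays as the existing rule, and report it beside the fold change from pre-booster. Keep the Day 1-referenced rate at post-booster visits if wanted, labelled as cumulative response since study entry.

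The cost is a sentence or two of SAP text, one derived flag and one table row. No new sample is needed: pre-booster Day 1 is already a sampling point with its own per-protocol rule (section 5.1.3). Few boosted women will contribute, so the interval will be wide. Because section 5.7.1.2 sets values above ULOQ to ULOQ, a woman whose pre-booster value exceeds a quarter of the ULOQ cannot show a 4-fold rise; a footnote giving the number of such women would cover this.
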